6.7.2.3 Objective 3: Incidence of AESI

The AESI evaluated in this study include the following categories: serious infections, opportunistic infections, hepatitis B reactivations, infusion related reactions, and malignancies. Analysis of AESI will include estimation of the cumulative incidence (i.e., risk), incidence rate, and time to AESI onset ([Table 5](#)). All analysis for AESI events (i.e., cumulative incidence, incidence rate and time-to-onset) will be performed using an intention-to-treat approach i.e., patients will be considered exposed regardless of subsequent discontinuation.

The cumulative incidence (with 95% CI) will be calculated separately for each AESI category considering the overall study population. For all AESI categories, except infusion related reactions, the cumulative incidence (with 95% CI) will be calculated as the total number of incident reports of AESI during the follow-up divided by the total number of patients. An algorithm to identify incident reports of AESI will be developed and described in the SAP. For infusion related reactions, the cumulative incidence (with 95% CI) will be calculated as the total number of all reports of infusion related reactions on the day of infusion (if date of inebilizumab administration is available) or during the first 3 days following prescription/dispensation (if date of inebilizumab administration is not available), divided by the total number of patients in the overall study cohort. Additional details of this calculation will be provided in the SAP.

The cumulative incidence estimates for each AESI category, except infusion related reactions, may also be calculated for shorter periods e.g., in monthly intervals after index date. In this case, the cumulative incidence in the first month after index date would consider patients with AESI reports in the first month in the numerator and patients with complete 12-month follow-up in the denominator. The cumulative incidence in the second month would consider patients with reports recorded only in the second month in the numerator and patients with complete 12-month follow-up included in the denominator. Due to the limited sample size, the time intervals may need to be clustered into e.g., 3-month intervals with the numerator and denominator adjusted accordingly. If sample size permits, the difference (with 95% CI) in cumulative incidence between 2 time periods of observation may be calculated.

The incidence rate and time to onset of AESI will be estimated in the overall study population. The incidence rates will be estimated separately for each AESI category, except infusion related reactions, as the total number of first reports of an AESI divided by the time at risk of the patients. The patients' time at risk will be counted from the initiation of inebilizumab treatment until occurrence of AESI, end of the 12-month follow-up or censoring. Incidence rate will be expressed as the number of first reports of an AESI per 1,000 patient-months.

Kaplan-Meier estimates of the median time from index date to AESI onset will be provided separately for each AESI category, except infusion related reactions, if number of events allows. If there is no AESI during the follow-up, the patient will be censored at the end of follow-up. Descriptive statistics on the time-to-event will be provided in further detail in the SAP.

Table 5 Overview of estimates of incidence and time to event defined for objective 3.

AESI category	Estimate	Time at risk	Event	Population
Infusion related reactions	Cumulative incidence	Day of infusion if date of inebilizumab administration available or 3 days following prescription/dispensation	All recorded reactions	Overall population
Serious Infections / Opportunistic infections	Cumulative incidence	12 months	All recorded infections during the follow-up	Overall population
	Cumulative incidence	Short periods	First infection during follow-up	Patients with complete 12-month follow-up
	Incidence rate	From index date to AESI, end of follow-up or censored*	First infection	Overall population
	Time to event	From index date to AESI end of follow-up or censor*	First infection	Overall population
Hepatitis B reactivations	Cumulative incidence	12 months	All recorded reactivations during the follow-up	Overall population
	Cumulative incidence	Short periods	First reactivation	Patients with complete 12-month follow-up
	Incidence rate	From index date to AESI end of follow-up or censor*	First reactivation	Overall population
	Time to event	From index date to AESI, end of follow-up or censor*	First reactivation	Overall population

AESI category	Estimate	Time at risk	Event	Population
Malignancies	Cumulative incidence	12 months	All recorded malignancies during the follow-up	Overall population
	Cumulative incidence	Short periods	First malignancy	Patients with complete 12-month follow-up
	Incidence rate	From index date to AESI end of follow-up or censor*	First malignancy	Overall population
	Time to event	From index date to AESI, end of follow-up or censor*	First malignancy	Overall population

* Censoring criteria will be the earliest of permanent treatment discontinuation, loss to follow-up (death, disenrollment/de-registering) or end of study period.

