- France: French National Health Data System (*Système National des Données de Santé* [SNDS]) and Multiple Sclerosis Registry (*Observatoire Français de la Sclérose en Plaques* [OFSEP])
- Germany: German Government Health Insurance (*Gesetzliche Krankenversicherung* [GKV])
- Italy: Italian Multiple Sclerosis and Related Disorders Registry (*Registro Italiano Sclerosi Multipla e Patologie Correlate* [RISM])
- The Netherlands: PHARMO Database Network
- Spain: Information System for Research in Primary Care (*Sistema d'Informació per al Desenvolupament de la Investigació en Atenció Primària* [SIDIAP])

Study size: In this study there is no a priori hypothesis testing and no prespecified sample size requirement. The final study size will be determined by the length of the study period and uptake of inebilizumab in the countries and population covered in the data sources. It is estimated that a pooled cohort of 400 NMOSD patients across data sources would enable a patient characteristic or AESI with an assumed incidence of 1% to be estimated with a precision of +/- 1% for 95% confidence interval (CI).

Data analysis:

Analyses will be performed for the overall study population and in sub-groups of special interest: patients concomitantly receiving other immunosuppressive agents and patients aged >65 years at index date.

To characterize new inebilizumab users, all patients of the study cohort will be described. Treatment patterns will be analysed only in patients with 12 months of complete follow-up and will be described as the number and proportion of patients who continue and discontinue treatment, respectively, who switch therapy and are exposed to add-on therapies. The median time to switching and the median time to use of add-on drugs will be described.

Estimation of the incidence will be conducted separately for each AESI category and will include cumulative incidence, incidence rate, and time to AESI onset. The cumulative incidence (with 95% CI) will be calculated as the total number of reports of an AESI during follow-up divided by the total number of patients initiating inebilizumab. The cumulative incidence estimates may also be calculated for shorter periods of time e.g., in monthly intervals after index date.

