6 RESEARCH METHODS

6.1 Study Design

This will be a non-interventional multi-center cohort study of patients initiating inebilizumab conducted with secondary data sources in France, Germany, Italy, the Netherlands, and Spain. The study will be based on a cohort-event monitoring design to capture both drug utilization and selected safety outcomes in patients initiating inebilizumab. The proposed study design allows for an efficient initial descriptive evaluation of AESI.

The **study period** in individual countries will start on different dates, depending on the launching time of the drug (the earliest in the second quarter of 2022) (Table 1). The end of the study period will be also country-specific (the latest in December 2027) and will depend on the dates of data availability in individual data sources (different lag times and data release dates).

Table 1 Study periods, by country

	France	Germany	Italy	Netherlands	Spain
	SNDS/ NOMADMUS	GKV	RISM	PHARMO	SIDIAP
Launch date (quarter, year)	Q2, 2022	Q3, 2022	Q2 2023	Q3, 2023	Q2, 2023
Start of study period	May 2022	Aug 2022	May 2023	Aug 2023	May 2023
End of study period	Dec 2026	Dec 2026	Dec 2027	Dec 2026	Sep 2027
Study period duration (months)	57	54	56	41	53

Q2, 2nd quartile; Q3, 3rd quartile

The study population will be constituted by a cohort of adult female and male patients diagnosed with NMOSD with entry trigger by inebilizumab initiation.

[figure not shown]
The **index date** (Day 0) will be defined as the date of first treatment (date of administration/prescription/dispensation, depending on data available in selected data sources) (Figure 1). Patients initiating the treatment will be identified throughout the study period. After the index date, enrolled patients will be followed for 12 months or censored at end of study period or loss of follow-up (death, disenrollment/de-registering) whichever occurs first.

A **baseline period**, including any time from when data are available up to the index date, will be used to establish comorbidities and NMOSD-related clinical characteristics, whereas a short period of 6 months prior to or at index date will be used to determine previous immunosuppressive therapies.

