6.9 Limitations of Research Methods

Automated healthcare databases are appropriate for real-world studies due to the recording of prescriptions and clinical data from routine clinical practice, independently of any study purposes.

The use of secondary data allows the identification of all drug users which limits selection bias, since all patients fulfilling the inclusion criteria are included in the study. Inebilizumab is available in secondary care settings (hospitals and specialized centers) which narrows down the area of searching for eligible patients. This is particularly relevant to answer the research objectives due to the fact NMOSD is a rare condition and inebilizumab is expected to be used by a small number of individuals. Furthermore, the

inclusion of several countries contributes to the representativeness of European inebilizumab users.

However, some limitations should be addressed:

- Inebilizumab is a novel drug, so one can expect changes over time in clinical practice regarding the use of the drug. The uptake of inebilizumab in the population covered by the data sources may be slow at the beginning of the study period and is likely to increase closer to the end. This pattern may result in a small sample of patients with complete follow-up, i.e., eligible to answer objectives 2 and 3. Thus, treatment patterns and safety outcomes may lack precision. Additionally, long-term treatment patterns and safety outcomes will not be assessed in this study.
- Despite the anticipated high reliability and validity of the data sources proposed for the study, there may be a potential of under- or misreporting of diagnostic information. In addition to variation in ICD-10 coding practices across countries, NMOSD is a rare and complex condition, with wide extent of the diagnostic work-up and diverse diseases can mimic NMOSD (39), making a late diagnosis or potential misclassification more probable. NMOSD-associated conditions may also be prone to misclassification, particularly the less severe ones, which may underestimate their frequency.
- Data collected for administrative purposes may be incomplete for medical information not directly related to reimbursement. This can affect the measurement of variables to characterize inebilizumab users and safety outcomes, underestimating its frequency. When available, the use of disease registries may minimize this limitation.

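### The 12-month AESI cumulative incidence is called a risk but defined as reports over all initiators: repeat reports inflate it and incomplete follow-up deflates it

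*Protocol*

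**What the plan says.** Section 6.7.2.3 announces "estimation of the cumulative incidence (i.e., risk), incidence rate, and time to AESI onset". For every category except infusion related reactions, the cumulative incidence is then "calculated as the total number of incident reports of AESI during the follow-up divided by the total number of patients", with an algorithm for incident reports left to the SAP. For infusion related reactions the numerator is all reports on the infusion day, or in a 3-day window where only prescription or dispensation is known.

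The abstract has the measure "calculated as the total number of reports of an AESI during follow-up divided by the total number of patients initiating inebilizumab", without the word *incident*. Table 5 gives the 12-month rows a time at risk of 12 months, the overall population, and as event "All recorded infections during the follow-up" or "All recorded malignancies during the follow-up", with a matching entry for hepatitis B reactivations. The short-period, rate and time-to-event rows of the same table use first events. The incidence rate is defined "as the total number of first reports of an AESI divided by the time at risk of the patients".

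On follow-up, section 6.1 states: "Patients initiating the treatment will be identified throughout the study period". Patients are followed for 12 months or until earlier censoring, including the end of the study period, and no minimum follow-up is required. Section 6.9 expects that uptake "may be slow at the beginning of the study period and is likely to increase closer to the end". It then describes patients with complete follow-up as the ones who can answer objectives 2 and 3.

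**The concern.** A 12-month risk is the probability that a patient has at least one event within 12 months. The protocol's ratio departs from this in two ways.

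- **Numerator.** It counts reports. A patient with two serious infections adds two, so the ratio estimates a mean number of reports per patient.
- **Denominator.** It counts every initiator in full, including those observed for only part of the 12 months. Their unobserved months are treated as event-free.

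The two errors run in opposite directions, so a reader of the final report could not tell whether a figure is too high or too low. The sources also disagree on the numerator (*reports*, *incident reports*, *all recorded*) and on the denominator (overall population in section 6.7.2.3 and Table 5, complete follow-up in section 6.9). A SAP cannot follow all of them. The precision statement in section 6.5 concerns proportions of patients, so it does not describe this ratio.

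**Working it through.** **1. The plan's own precision figures.** With n = 1.96² × p(1−p)/d²:

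- p = 1%, d = 1%: 3.8415 × 0.0099/0.0001 = 380 (Table 3: 380).
- p = 4%, d = 2%: 3.8415 × 0.0384/0.0004 = 369 (Table 3: 369).
- At 400 patients the half-widths are 0.98% at p = 1% and 1.92% at p = 4%.

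All 30 filled cells of Table 3 reproduce. They are figures for a single proportion, with each patient counted once and fully observed.

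**2. Shortfall from incomplete follow-up.** Inputs are the study period lengths T in months as printed in Table 1. Assumptions are mine: constant hazard, a rare event, and no censoring other than the end of the study period. A patient entering s months before the end (s < 12) loses the fraction 1 − s/12 of follow-up.

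- Uniform entry: mean loss = (1/T)∫₀¹²(1 − s/12)ds = 6/T; share without 12 months = 12/T.
- Entry rising linearly from zero: mean loss = (2/T²)∫₀¹²(1 − s/12)(T − s)ds = (12T − 48)/T²; share without 12 months = 1 − ((T − 12)/T)².

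| Country | T | Loss, uniform | Loss, rising | Without 12 months, uniform / rising |
|---|---|---|---|---|
| France | 57 | 10.5% | 19.6% | 21% / 38% |
| Germany | 54 | 11.1% | 20.6% | 22% / 40% |
| Italy | 56 | 10.7% | 19.9% | 21% / 38% |
| Netherlands | 41 | 14.6% | 26.4% | 29% / 50% |
| Spain | 53 | 11.3% | 20.9% | 23% / 40% |

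Exact calculation with hazard −ln(1 − risk)/12 and first events only, over all initiators:

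| True risk | T = 57, uniform / rising | T = 41, uniform / rising |
|---|---|---|
| 1% | 0.89% / 0.80% | 0.85% / 0.74% |
| 4% | 3.58% / 3.22% | 3.42% / 2.95% |

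An estimator that handles censoring targets the true 1% or 4%.

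**3. Inflation from repeat reports.** If an affected patient has on average m reports, the ratio is m × risk at full follow-up. The documents give no value for m. Assuming 1.2, 1.5 or 2.0, a 4% risk reads as 4.8%, 6.0% or 8.0%.

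**4. Both together.** With the French follow-up factors 0.895 (uniform) and 0.80 (rising), and m from 1.0 to 2.0, the ratio lies between 1.0 × 0.80 = 0.80 and 2.0 × 0.895 = 1.79 times the true risk. The errors cancel at about m = 1/0.895 = 1.12 or m = 1/0.80 = 1.25. The sign of the net error therefore depends on a quantity the protocol does not supply.

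**5. Does another planned output give the risk?**

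- Kaplan-Meier is planned only for the median time to onset, which needs half the patients to have an event. At risks of 1–4% it will not be reached.
- The short-period figures use first events in patients with complete follow-up. That is a different event and population, so they need not add up to the 12-month figure.
- The incidence rate counts first reports over time at risk and avoids both errors, but it is a rate.

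**The case against.** The strongest reply has four parts.

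- **The SAP algorithm.** An algorithm for incident reports could remove repeat coding of one episode. It would not limit a patient to one event, and it cannot be squared with *all recorded* in Table 5. Inflation is probably small for malignancies and hepatitis B reactivations; it matters mainly for serious and opportunistic infections. Infusion related reactions are also open to repeat counting, since all reports count and section 6.3.3 allows three infusions in 12 months, but the shortfall calculation does not apply to their short window.
- **The incidence rate.** Under constant hazard it converts to a 12-month risk. That is true, but the conversion is not planned. Section 6.1 also wants short-period estimates because frequency may vary over follow-up, so the plan does not itself assume constant hazard.
- **Size.** The shortfall is relative. At 1% risk it is 0.11 to 0.26 percentage points against a planned ±1, and at 4% it is 0.42 to 1.05 against ±2. The 26% is the Netherlands under a linear ramp. France and Italy make up (53.2 + 39.9)/110.7 = 84% of the Table 4 population, and their range is about 10–20%. Section 6.9 supports rising uptake but not a linear shape, and early events would shrink the shortfall. This all stands, and it bears on how large the error is. The definition remains wrong.
- **Stronger readings.** A reader might infer that the protocol prescribes a binomial interval for this ratio. It promises a 95% CI without a method; the normal approximation in section 6.5 is stated for sample size, and leaving the interval method to the SAP is no fault. A reader might also take this for the main safety estimate, but section 6.7.2.3 ranks none of its three measures and the ENCePP checklist marks primary and secondary outcomes as not applicable. A ratio above 1 is possible in principle but remote at the planned incidences.

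**Conclusion.** The concern holds. Followed as written, the protocol reports a figure labelled a 12-month risk that is not one. Incomplete follow-up lowers it by about 10–15% (uniform entry) or 20–26% (linearly rising entry) in relative terms, given constant hazard and administrative censoring only over the Table 1 periods. Repeat reports raise it by an unknown amount; the values of m used above are illustrations. The documents do not support any claim about the net direction. The disagreement between the abstract, section 6.7.2.3, Table 5 and section 6.9 rests on no assumption. The ±1% at 1% in section 6.5 applies only to a proportion of patients with a first event and complete follow-up.

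**What to change.** - **All categories except infusion related reactions.** Define cumulative incidence as the probability of a first event in the category by month 12, in the overall population, estimated with censoring handled: 1 minus Kaplan-Meier, or Aalen-Johansen with death as a competing event. The protocol gives no death rate to show that the choice matters, but it should be named in advance.
- **Table 5.** Change *all recorded* to *first* in the 12-month rows for these categories.
- **Alignment.** Use the same numerator and population in the abstract, section 6.7.2.3, Table 5 and section 6.9.
- **Infusion related reactions.** Count patients with at least one reaction in the stated window if the figure is called a risk, or rename it reports per patient.
- **Total burden.** If wanted, report recurrent events separately per person-time.
- **Section 6.5.** State that the precision figures refer to patients with a first event and complete follow-up.

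The CI method may stay with the SAP, but it must suit the chosen estimator and allow for zero events, which are plausible when analyses run by data source. A log-log interval, for example, is undefined there.

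The cost is protocol wording, some extra analysis in each source and slightly wider intervals. Event dates are already to be retrieved (section 6.3.4). Small-number masking may limit how much event-time detail a source can release.

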6.7.2.2 Objective 2: Treatment patterns of inebilizumab

The number and proportion of patients in the overall study population receiving the drug, and by dose stratification, (below or above the recommended dose in the product characteristics [300 mg/IV infusion]) will be reported at each of the first, second, and third infusion. Additionally, the number and proportion of patients who change dose between the individual infusions as well as the time (in days) between the first and each subsequent treatment (regardless of dose) will be reported.

Inebilizumab treatment patterns, as described below, will be assessed in the period of 12 months from index date and only patients with a complete 12-month follow-up, regardless of inebilizumab discontinuation, will be considered.

The number and proportion of patients who experience the following treatment pattern related events will be reported separately for each of the events: continuous and discontinuous treatment, switching, use of add-on therapies, according to what is defined in [section 6.3.3](#). For all the events, the denominator consists of all patients exposed to inebilizumab and followed for the full 12-month period.

The median time to switching and the median time to use of add-on drugs will be described in the subgroups of switchers and patients using add-on therapies (as defined in [section 6.3.3](#)), respectively. For the subgroup of switchers (as defined in [section 6.3.3](#)), the time to switch will be calculated as the time from the index date until the first recorded start date of another NMOSD maintenance drug. For the subgroup of patients using add-on therapies (as defined in [section 6.3.3](#)), the time to add-on drug use will be calculated as the time from the index date until the first recorded start date of an add-on drug.

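### Short-period AESI risks are divided by patients who later complete 12 months of follow-up, so month-1 risk depends on later survival and observation

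*Protocol*

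**What the plan says.** Protocol section 6.7.2.3 defines the month-1 cumulative incidence with "patients with AESI reports in the first month in the numerator and patients with complete 12-month follow-up in the denominator". Month 2 follows the same pattern: "patients with reports recorded only in the second month in the numerator and patients with complete 12-month follow-up included in the denominator". In Table 5 the short-period rows for serious and opportunistic infections, hepatitis B reactivations and malignancies all give the population as "Patients with complete 12-month follow-up". Infusion related reactions have no short-period row.

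Section 6.1 sets the follow-up rule: "enrolled patients will be followed for 12 months or censored at end of study period or loss of follow-up (death, disenrollment/de-registering) whichever occurs first". It also states: "Patients initiating the treatment will be identified throughout the study period". Accrual does not stop 12 months before the country's end date.

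The status of these estimates varies. Section 6.7.2.3 and the abstract make them optional. Section 6.1 says they will be produced, in order to show periods of higher or lower frequency. Section 6.7.2.3 also allows a difference between two periods with a 95% CI.

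Section 6.9 expects slow early uptake that rises towards the end, leaving "a small sample of patients with complete follow-up, i.e., eligible to answer objectives 2 and 3". It names loss of precision as the consequence, but not selection.

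**The concern.** A month-1 risk needs everyone at risk when month 1 begins. Here, membership of the denominator depends on months 2 to 12, and one way to lose membership is to die of the event being counted.

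The text and Table 5 also leave the numerator in two states. Table 5 restricts the whole analysis population to completers, while the sentences in section 6.7.2.3 restrict only the denominator. The first version removes fatal cases. The second has a numerator that is not a subset of its denominator. The two errors run in opposite directions, so a reader of the report could not tell which way a monthly figure is wrong.

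These estimates are the study's means of locating periods of higher risk after initiation, and the rule is least reliable for the most severe events.

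**Working it through.** **The plan's own figure.** The protocol gives no figure for the short-period estimates. Its precision basis (section 6.5, Table 3) reproduces: n = 1.96² × 0.01 × 0.99 / 0.01² = 380.3, against 380 stated. At n = 400 the half-width for a 1% incidence is 0.98%.

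**Inputs.** Study period T from Table 1: France 57, Germany 54, Italy 56, Netherlands 41, Spain 53 months. Covered adults from Table 4, in millions: 53.18, 5.0, 39.91, 7.0, 5.6 (total 110.69). Assumptions: uptake is proportional to covered adults, and its time course is either uniform or a linear ramp from zero (in the spirit of section 6.9). Case fatality and other losses are not in the documents.

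**Step 1: share of initiators who start in the last 12 months.**

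| | Uniform, 12/T | Ramp, 1 − ((T−12)/T)² |
|---|---|---|
| France | 21% | 38% |
| Germany | 22% | 40% |
| Italy | 21% | 38% |
| Netherlands | 29% | 50% |
| Spain | 23% | 40% |
| Weighted by Table 4 | 21.8% | 38.9% |

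Of 400 initiators, about 313 (uniform) or 245 (ramp) remain. The half-width for a 1% risk widens from 0.98% to 1.10% or 1.25%.

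**Step 2: numerator and denominator both limited to completers (Table 5).** Take 400 patients, a true risk of 5% (20 cases) and 4 other deaths, with case fatality f. The estimate is 20(1−f)/(400 − 20f − 4):
- f = 10%: 18/394 = 4.6%
- f = 20%: 16/392 = 4.1%
- f = 40%: 12/388 = 3.1%

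On a more monthly scale, with a true month-1 risk of 1.0%, the estimate is 0.01(1−f)/(0.01(1−f) + 0.99). This gives 0.90, 0.80, 0.70 and 0.50% for f = 10, 20, 30 and 50%. Late starting and other loss cancel here if they are unrelated to the event.

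**Step 3: only the denominator limited (text of section 6.7.2.3).** Ignoring deaths, the inflation is about 1/(1 − share lost):
- Weighted: 1/(1 − 0.218) = 1.28 uniform; 1/(1 − 0.389) = 1.64 ramp.
- Netherlands alone: 41/29 = 1.41 uniform; (41/29)² = 2.0 ramp.

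These are slight upper values for month 1, because patients who start in the final month do not have a full month observed. With uniform uptake and constant risk, the factor for month k is (T − k + 0.5)/(T − 12). For France this is 56.5/45 = 1.26 in month 1 and 45.5/45 = 1.01 in month 12. A constant risk would thus appear to fall over the year.

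**The case against.** **Reach.** The 12-month cumulative incidence, incidence rate and Kaplan-Meier analyses all use the overall population, and fatal AESI count in each. A reader might infer that fatal events vanish from the study's safety results; the documents do not support that. Only the short-period rows, and any between-period difference built on them, are affected. This stands. Optionality is a weaker defence, because section 6.1 says the estimates will be produced.

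**Late starters.** Under the Table 5 reading, excluding them mainly costs precision, unless risk changes with calendar time, and section 6.9 already discloses that loss. This also stands.

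**Size.** The 1.41- and 2.0-fold figures belong to the Netherlands alone, about 6% of covered adults (7.0 of 110.7 million). The 5% risk used for survivor bias is closer to a yearly than a monthly risk, and no document gives a case fatality. If fatality were similar across months and death prompt, the contrast between months would largely survive under the Table 5 reading. It would not under the literal reading, where the inflation itself declines month by month.

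**Later-month denominators.** A reader might infer that keeping earlier cases in them is a further error. It is not: first events in month k over a fixed starting cohort form a valid unconditional increment of cumulative incidence.

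**Objective 2.** Section 6.7.2.2 states that "only patients with a complete 12-month follow-up, regardless of inebilizumab discontinuation, will be considered". A reader might extend the criticism there. That restriction is disclosed and separate, and permanent discontinuation is defined by the absence of further treatment during follow-up (section 6.3.3), which needs the full window to classify.

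**Table 5 footnote.** It adds permanent discontinuation to the censoring criteria. A reader might infer that discontinuers also lose complete follow-up, but the asterisk is attached only to the incidence-rate and time-to-event rows.

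**Conclusion.** The point holds for the short-period AESI cumulative incidence only. The protocol itself fixes the rule, so it has not been left to the SAP.

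Under the Table 5 reading the risk is biased downward by the loss of fatal cases. The direction follows from the definitions; the size depends on case fatality and is illustrative (a true 5% becomes 4.6, 4.1 or 3.1% at 10, 20 or 40%).

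Under the literal reading of section 6.7.2.3 early-interval risk is biased upward, by about 1.28-fold with uniform uptake or 1.6-fold with a linear ramp. These factors assume uptake proportional to covered adults and no deaths.

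The text and Table 5 must be reconciled in either case. Section 6.9 also needs correction, because it treats complete follow-up as a condition for Objective 3 although the other Objective 3 measures use the overall population.

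**What to change.** In the Table 5 short-period rows, replace the completer population with the overall population. Rewrite the corresponding sentences in section 6.7.2.3 around one stated estimand. The preferred choice is the increment of the cumulative incidence function over each interval in all initiators, with censoring at end of observation and death as a competing event (Aalen-Johansen).

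The alternative is the interval rate: first events in the interval divided by the person-time of patients alive, under observation and free of that AESI. The increment is unconditional and the rate is conditional on being event-free, so choose one and name it.

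Align sections 6.1, 6.7.2.3 and 6.9 on whether these estimates will or may be produced and on which patients contribute. Objective 2 needs no change for this point.

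The data are the same, and the numbers contributing to early intervals rise. The cost is a small amount of extra programming in each data source.
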